Appendix D Investigator Consent to Use of Personal Information

Takeda will collect and retain personal information of investigator, including his or her name, address, and other personally identifiable information. In addition, investigator's personal information may be transferred to other parties located in countries throughout the world (eg, the United Kingdom, United States, and Japan), including the following:

- Takeda, its affiliates, and licensing partners.
- Business partners assisting Takeda, its affiliates, and licensing partners.
- Regulatory agencies and other health authorities.
- IRBs and IECs.

Investigator's personal information may be retained, processed, and transferred by Takeda and these other parties for research purposes including the following:

- Assessment of the suitability of investigator for the study and/or other clinical studies.
- Management, monitoring, inspection, and audit of the study.
- Analysis, review, and verification of the study results.
- Safety reporting and pharmacovigilance relating to the study.
- Preparation and submission of regulatory filings, correspondence, and communications to regulatory agencies relating to the study.
- Preparation and submission of regulatory filings, correspondence, and communications to regulatory agencies relating to other medications used in other clinical studies that may contain the same chemical compound present in the study drug.
- Inspections and investigations by regulatory authorities relating to the study.
- Self-inspection and internal audit within Takeda, its affiliates, and licensing partners.
- Archiving and audit of study records.
- Posting investigator site contact information, study details and results on publicly accessible clinical trial registries, databases, and websites.

Investigator's personal information may be transferred to other countries that do not have data protection laws that offer the same level of protection as data protection laws in investigator's own country.

Investigator acknowledges and consents to the use of his or her personal information by Takeda and other parties for the purposes described above.

Appendix E Collection, Storage, and Shipment of PK Samples

Instructions for Processing of Plasma Samples for PK Analysis of Alogliptin and Pioglitazone

1. Collect 6 mL of venous blood into a chilled Becton-Dickinson Vacutainer. All alogliptin and pioglitazone blood samples should be collected into vacutainers containing K₂EDTA.
2. Gently invert the vacutainer several times to mix the additive with the collected blood prior to centrifugation and place immediately on ice.
3. Centrifuge the vacutainers for 10 minutes at approximately 1100 to 1300 relative centrifugal force (RCF) at room temperature. Note: if using a collection device other than Becton-Dickinson, refer to manufacturer's instruction for proper centrifugation force and time.
4. Immediately following centrifugation, gently remove plasma from the packed cells. To ensure a more homogeneous sample, all plasma should first be transferred into 1 aliquot. From there, split the plasma evenly between the 4 aliquots. A minimum of 0.5 mL needs to be obtained for each sample. Labeling may include protocol number (Alogliptin-1002), sample matrix (ie, plasma), analyte (alogliptin or pioglitazone), randomization sequence number, period, nominal day and time, and either "SET 1" (for original sample) or "SET 2" (for duplicate sample). Note: the "SET 1" samples should be transferred first and then the "SET 2" tubes transferred.
5. Cap the labeled storage tubes and freeze the plasma samples immediately at approximately -20°C or lower until shipment. No more than 45-60 minutes will elapse between blood collection and freezing the plasma sample.

Shipping of Plasma Samples Alogliptin and Pioglitazone

The following instructions are recommended unless they differ from the site's standard operating procedures for labeling, packaging, or shipping of PK samples.

1. Biological samples (plasma) should be shipped on dry ice to prevent thawing during transit. Samples should be shipped only on Monday, Tuesday, or Wednesday, and at least 2 days prior to a national holiday, in order to minimize the possibility of samples in transit over a weekend or holiday. If duplicate samples are to be shipped, send SET 1 samples and await confirmation of arrival before shipping the duplicate SET 2 samples.
2. Before shipping, make sure the sample tubes are tightly sealed. Separate each subject's samples as follows:
3. Separate the duplicate SET 2 samples from the SET 1 samples.
4. Place SET 1 samples for each subject into self-sealing bag (eg, Ziploc) containing additional absorbent material.
5. Using a permanent marker, write the 4-digit randomization sequence number, sample matrix (ie, plasma), number of samples, and "SET 1" on each self-sealing bag.
6. Place the bags of individual subject's samples into a larger plastic bag so that samples are double bagged. Duplicate SET 2 samples should be returned to the freezer for storage. Repeat

steps 3 through 6 above when preparing duplicate samples for shipment, except self-sealing bags should be marked "SET 2."

7. An inventory of individual samples should accompany each shipment and should include the Sponsor's name (Takeda), study medication (alogliptin, pioglitazone), protocol number (Alogliptin-1002), investigator's name, sample type (ie, plasma) analyte (alogliptin, pioglitazone), subject randomization sequence number, period, nominal collection day and time, and intended sample storage conditions. When duplicate SET 2 samples are being shipped, make a copy of the original SET 1 sample inventory and mark as "SET 2." Place the inventory paperwork into a large self-sealing bag. SET 1 samples will be shipped first on dry ice, followed by shipment of duplicate SET 2 samples after SET 1 samples have been received by the analytical laboratory.
8. For sample packing, utilize dry ice generously (eg, 20-25 pounds per day of transit) to safeguard against longer than expected shipping times and delays. Use newspaper or other material to insulate the double-bagged samples from direct contact with the dry ice. Place the sample bundles into a Styrofoam container (or other suitable container) and fill the excess space with dry ice slabs or ice pellets (preferably the latter). Make a note of the estimated weight of the dry ice used per shipping container.
9. Place the inventory paperwork (in a large self-sealing bag) on top of the dry ice in the Styrofoam container. Place the lid on the Styrofoam container and seal completely with strapping tape. Place the Styrofoam container in a cardboard shipping carton and seal securely with strapping tape.
10. Mark the outside of shipping carton(s) with a tally number (eg, 1 of 5, 2 of 5).
11. Affix an address label to each shipping carton. Complete the address label with the following information:

Plasma samples for alogliptin and pioglitazone

PPD

Affix a carbon dioxide label on each carton, specifically:

Carbon Dioxide Solid UN-1845

Class 9 PKG GR III

Quantity _____

(fill in weight to nearest lb/kg and specify unit of measure used)

12. Affix 2 dry ice symbol labels on opposite sides of the carton. Mark **KEEP FROZEN** on each carton. Specify a return address and contact person on the carton.

13. Obtain the airway bill number and a receipt of shipment from the carrier.
14. After shipping of the samples, please contact the bioanalytical laboratory.

For alogliptin and pioglitazone plasma samples, please contact:

PPD

15. When calling, provide the following information:

- Name of courier or transport company
- Time and date the shipment left the clinical site
- Airway bill number

Appendix F Detailed Description of Amendments to Text

The primary sections of the protocol affected by the changes in Amendment No. 02 are indicated. The corresponding text has been revised throughout the protocol.

Change 1: Revised descriptions of study drugs to align with local requirements.

The primary change occurs in Section 8.1.1 Dosage Form, Manufacturing, Packaging, and Labeling.

Initial wording:	
In this protocol, the term study medication refers to:
 
• Alogliptin 25 mg tablets (commercially available on the Russian market).• Pioglitazone 15 and 30 mg tablets manufactured by Takeda, Japan and sourced as commercial packs from the commercial market.• Alogliptin/Pioglitazone FDC 25/15 mg and 25/30 mg tablets manufactured by Takeda, Japan and sourced as commercial packs from the commercial market. 
All medication sourced by the Sponsor as defined below.
 
• Commercial alogliptin 25 mg tablets, locally available on the Russian market.• Commercial pioglitazone 15 and 30 mg tablets (in commercial packs).• Commercial alogliptin/pioglitazone FDC 25/15 mg tablets and 25/30 mg tablets (in commercial packs). 
Each commercial pack supplied will be labeled with a single panel open computer-generated label containing the required information.

Amended or new wording:	
In this protocol, the term study medication refers to:
 
• Alogliptin 25 mg film-coated tablets No. 28 (commercially available on the Russian market) manufactured by Takeda (product released by Takeda Ireland).• Pioglitazone 15 and 30 mg tablets No. 30 manufactured by Pliva Hrvatska d.o.o., Croatia Takeda, Japan and sourced as commercial packs from the commercial market of Croatia.• Alogliptin/Pioglitazone FDC 25/15 mg film-coated and 25/30 mg tablets No. 28 manufactured by Takeda, Japan (product released by Takeda Ireland), Japan and sourced as commercial packs from the commercial market under the name NesinaAct. For this clinical study, NesinaAct will be supplied to the site as commercial packs and labeled as SYR-322-4833 BL 25/15.• Alogliptin/Pioglitazone FDC 25/30 mg film-coated tablets No. 28 manufactured by Takeda (product released by Takeda Ireland) and sourced as commercial packs from the commercial market under the name

Incesync. For this clinical study, Incesync will be supplied to the site as commercial packs and labeled as SYR-322-4833 BL 25/30.

All medication sourced by the Sponsor as **follows**: ~~defined below.~~

- Commercial alogliptin 25 mg tablets; **sourced** locally ~~available on~~ **from** the Russian market.
- Commercial pioglitazone 15 and 30 mg tablets **sourced locally from the Croatian market** ~~(in commercial packs).~~
- Commercial alogliptin/pioglitazone FDC 25/15 mg tablets and 25/30 mg tablets ~~(in commercial packs)~~ **sourced from Takeda and labeled as SYR-322-4833 BL 25/15 and SYR-322-4833 BL 25/30, respectively.**

Each commercial pack supplied will be labeled with a single panel open computer-generated label containing the required information **including information “For clinical trial only”**.

The following sections also contain this change:

- Section [8.1.1.1 Study Drug](#).
- Section [8.1.1.2 Sponsor-Supplied Drug](#).

Change 2: [Corrected inconsistency in length of pregnancy monitoring time after the end of the study.](#)

The primary change occurs in Section [7.2 Exclusion Criteria](#).

Initial wording:	11. If female, the subject is pregnant (confirmed by a positive pregnancy test) or lactating or intending to become pregnant before, during, or within 30 days after participating in this study; or intending to donate ova during such time period.
------------------	---

Amended or new wording:	11. If female, the subject is pregnant (confirmed by a positive pregnancy test) or lactating or intending to become pregnant before, during, or within 30 35 days after participating in this study; or intending to donate ova during such time period.
-------------------------	--

Rationale for Change:

Corrected inconsistency in length of pregnancy monitoring time after the end of the study.

The following section also contain this change:

- [Appendix C](#) Elements of the Subject Informed Consent (item 24).

[figure not shown]
Change 3: [Updated information for shipping label and contact information for the bioanalytical laboratory.](#)

The primary change occurs in [Appendix E Collection, Storage, and Shipment of PK Samples](#).

Initial	11. Affix an address label to each shipping carton. Complete the address label with the
---------	---

wording: following information:

Plasma samples for alogliptin
PPD

Plasma samples for pioglitazone
PPD

[figure not shown]

14. After shipping of the samples, please contact the bioanalytical laboratory.

For alogliptin plasma samples, please contact:
PPD

[figure not shown]

For pioglitazone plasma samples, please contact;
PPD

3.0 LIST OF ABBREVIATIONS

| | |
|------------------|--|
| AE | adverse event |
| ALT | alanine aminotransferase |
| ANOVA | analysis of variance |
| AST | aspartate aminotransferase |
| AUC | area under the curve |
| BMI | body mass index |
| C _{max} | maximum concentration |
| CPK | creatine phosphokinase |
| CV | coefficient of variation |
| ECG | electrocardiogram |
| eCRF | electronic case report form |
| GGT | γ-glutamyl transferase |
| ICF | informed consent form |
| HIV | human immunodeficiency virus |
| LLN | lower limit of normal |
| MAV | markedly abnormal value |
| MedDRA | Medical Dictionary for Regulatory Activities |
| PK | pharmacokinetics |
| SAE | serious adverse event |
| ULN | upper limit of normal |
| WHODrug | World Health Organization Drug Dictionary |

4.0 OBJECTIVES

4.1 Primary Objectives

To assess the relative bioavailability and bioequivalence of 2 strengths of the fixed-dose combination tablet product SYR-322-4833 BL compared to the individual alogliptin and pioglitazone tablets in healthy Russian subjects

4.2 Secondary Objectives

None

4.3 Additional Objectives

To perform a comparative analysis of AE data after the administration of SYR-322-4833 BL and after coadministration of alogliptin and pioglitazone to healthy volunteers within the scope of the trial.

4.4 Study Design

This is a single-center, open-label, randomized, 4-sequence, 4-period, single dose crossover study involving 72 healthy adult, male and female subjects between the ages of 18 and 55 years, inclusive.

Subjects will be randomized in the order in which they are enrolled into the study. The 72 eligible subjects will be randomized to 1 of 4 drug intake sequences in a 1:1:1:1 ratio. Due to the large sample size, volunteers may be divided into 2 or 3 cohorts according to space limitations at the site. All cohorts will be dosed sequentially.

The study consists of a Screening Period (Days -28 to Day-2) and 4 Drug Intake Periods. A washout interval of 7 days (beginning immediately after dosing on Day 1) will separate the doses of each study period. Subjects will be admitted into the clinic on Day -1 (Day 7 of the preceding period for Periods 2, 3, and 4) and will be dosed on Day 1 of each period. Starting on Day 1 of each period, blood samples for determination of alogliptin and pioglitazone plasma concentrations will be collected predose through 72 hours postdose. The subjects will be discharged from the clinic after the 24-hour blood sample collection on Day 2 of each period and will return to the clinic for the 36-hour blood sample collection on Day 2 and on Days 3 and 4 of each period to complete study procedures. Final Visit procedures will be performed on Day 4 of Period 4 and a Follow-up call will be made 14 days \pm 2 days following the last dose of study drug.

A schematic of the study design is included as [Figure 1](#). A schedule of assessments is listed in [Appendix A](#).

Figure 1 Schematic of Study Design

| Predose Period | | | Drug Intake Period (c) | | | | | | | |
|----------------|--------------|---------------------|------------------------|----------------------|--------------|----------------------|--------------|----------------------|------------------|-------------|
| Screening (a) | Check-in (b) | | Period 1 | | Period 2 | | Period 3 | | Period 4 | |
| Days -28 to -2 | Day -1 | | Day 1 Dosing | Days 2 to at least 7 | Day 1 Dosing | Days 2 to at least 7 | Day 1 Dosing | Days 2 to at least 7 | Day 1 (d) Dosing | Days 2 to 3 |
| | | Sequence I (n=18) | A | WO | B | WO | C | WO | D | WO |
| | | Sequence II (n=18) | B | | C | | D | | A | |
| | | Sequence III (n=18) | C | | D | | A | | B | |
| | | Sequence IV (n=18) | D | | A | | B | | C | |

A=SYR-322-4833 BL (25 mg + 15 mg) (test regimen), B=alogliptin 25 mg + pioglitazone 15 mg (reference regimen), C=SYR-322-4833 BL (25 mg + 30 mg) (test regimen), D=alogliptin 25 mg + pioglitazone 30 mg (reference regimen), ET=Early Termination, WO=Washout of 7 days between dosing.

(a) Screening may consist of 1 or more visits. Subjects will sign an informed consent form at the first visit and return to the clinic in a fasted state for safety laboratory testing at the second visit.

(b) Subjects are admitted into the clinic on Day -1 of each period (~Day 7 of the preceding period for Periods 2, 3, and 4).

(c) Randomization occurs on Day 1 of Period 1. Subjects check out of the unit on Day 2 following the 24-hour blood sample collection but return to the clinic for the 36-hour blood sample collection on Day 2 and on Days 3 and 4 of each period to complete study procedures.

(d) Follow-up call will be made 14 days ±2 days following the last dose of study drug.

5.0 ANALYSIS ENDPOINTS

5.1 Primary Endpoints

The following plasma pharmacokinetic (PK) parameters of alogliptin and pioglitazone will be derived on Day 1 of each period:

- Maximum observed concentration (C_{max}).
- Area under the concentration-time curve from the time 0 to time 72 hours (AUC_{72}).

5.2 Additional Endpoints

- CCI [REDACTED]
- Percentage of subjects who experience at least 1 postdose AE.
- Percentage of subjects who have clinically significant changes in laboratory tests at least once postdose.
- Percentage of subjects who have clinically significant changes in vital sign measurements at least once postdose.
- Percentage of subjects who have clinically significant changes in electrocardiogram (ECG) parameters at least once postdose.
- Percentage of subjects who experience at least 1 postdose event of hypoglycemia.

6.0 DETERMINATION OF SAMPLE SIZE

A sample size of 72 subjects (18 per sequence) will be enrolled in this 4-period, 4-sequence crossover study. The sample size is appropriate to assess the bioavailability of alogliptin and pioglitazone from the fixed dose combination relative to the individual tablets and also provide greater than 80% power for C_{\max} of pioglitazone establishing bioequivalence between regimens for both strengths (SYR-322-4833 BL 25 mg+15 mg and SYR-322-4833 BL 25 mg+30 mg). This is based on acceptance ranges of 80% to 125%, the intra-subject variability (%CV) of 33% for C_{\max} of pioglitazone; the expected ratios of the central values for C_{\max} are between 0.95 and 1.05, and drop-out rate of 14%. Since the intra-subject variability for pioglitazone AUC_t , and alogliptin C_{\max} and AUC_t is less than 33%, the power for assessing bioequivalence for pioglitazone AUC_t and alogliptin C_{\max} and AUC_t are each greater than 80% for both strengths.

7.0 METHODS OF ANALYSIS AND PRESENTATION

7.1 General Principles

Continuous data will be summarized using descriptive statistics, including the number of subjects, mean, standard deviation (SD), median, minimum, and maximum. The coefficient of variation (%CV) and geometric mean will be included in the summary of continuous data where indicated. Categorical data will be tabulated as the number and percentage of subjects in each category; unless otherwise specified the denominator for percentage is total number of subjects with non-missing data.

Arithmetic means, geometric means, and medians will be presented to 1 more decimal place than the recorded data, and SDs will be presented to 2 more decimal places than the recorded data, where appropriate. Where applicable, confidence intervals about a parameter estimate will be presented using the same number of decimal places as the parameter estimate and p-values will be rounded to 3 decimal places prior to assessment of statistical significance.

All study-related raw data for enrolled subjects, including derived data, will be presented in data listings. In addition, the actual day relative to the first dose will be presented, where applicable.

All statistical analyses will be performed using the SAS System® Version 9.4.

7.1.1 Study Definitions

Generally, Baseline is defined as the value or observation prior to first dose of study drug, i.e. Day 1 Period 1. Where applicable, pre-dose values will be obtained for each dosing Period.

7.1.2 Definition of Study Days

Study Day 1 is defined as the date of the first dose of study drug, as recorded on the electronic case report form (eCRF) dosing page. Other study days are defined relative to Study Day 1, with Day 1 being Study Day 1 and Day -1 being the day prior to Study Day 1. Study days prior to the first dose of study drug will be calculated as: {date of assessment/event – date of first dose of study drug}. Study days on or after the first dose of study drug will be calculated as: {date of assessment/event – date of first dose of study drug + 1}. The calculation of day within a period will be similar to study day but relative to the date of administration of the first dose of study drug within the period.

7.1.3 Definition of Study Visit Windows

All blood samples should be identifiable by date and time. If actual time is missing then the nominal time may be used in the analyses. Safety laboratory collections (i.e. clinical laboratory evaluations) are obtained Pre-dose on Day 1 (baseline) and Day 4 of Period 4 (post-baseline). If a subject has more than one laboratory value (eg. a repeat laboratory draw) then the latter will be used for data analyses.

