If subjects experience ALT or AST >3 ×upper limit of normal (ULN), follow-up laboratory tests (at a minimum, serum alkaline phosphatase, ALT, AST, total bilirubin, GGT, and international normalized ratio [INR]) should be performed within a maximum of 7 days and preferably within 48 to 72 hours after the abnormality was noted. (Refer to Section 10.2.3 for the appropriate guidance on reporting abnormal liver function tests.)

If the ALT or AST remains elevated >3 ×ULN on these 2 consecutive occasions, the investigator must contact the Medical Monitor for consideration of additional testing, close monitoring, possible discontinuation of study drug, discussion of the relevant subject details and possible

alternative etiologies. The abnormality should be recorded as an AE (please refer to Section 10.2.3 for reporting requirements).

The investigator will maintain a copy of the laboratory accreditation and the reference ranges for the laboratory used.

Laboratory reports must be signed and dated by the investigator indicating that the report has been reviewed and any abnormalities have been assessed for clinical significance.

All laboratory abnormalities must be recorded as an AE in the subject's source documents and on the appropriate eCRF. A clinically significant laboratory abnormality that has been verified by retesting will be followed until the abnormality returns to an acceptable level or a satisfactory explanation has been obtained.

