13.1.4 Subject Condition Assessments

Subject condition assessments will be performed using the Safety Set. All subject condition assessments, including AEs, clinical laboratory evaluations, 12-lead ECG results, and vital signs will be summarized with descriptive statistics, where appropriate, and presented in the data listings.

All AEs will be coded using MedDRA and presented in the data listings.

A postdose AE is defined as an AE that occurs after the subject receives the first dose of study medication and within 30 days after the last dose of study medication is received. Summary of AEs will include numbers and percentages of subjects experiencing AEs by system organ class and preferred term. AEs will also be summarized based on their intensity and relationship to study medication by system organ class and preferred term. If a subject has more than 1 AE that codes to the same preferred term, the subject will be counted only once for that preferred term within regimen. Similarly, if a subject has more than 1 AE within a system organ class category, the subject will be counted only once in the system organ class category within the regimen. In the intensity summary, a subject will be counted only in the highest intensity category for each preferred term and each organ class. In the relationship to study medication summary, a subject will be counted only in the highest relationship category for each preferred term and each system organ class. Each summary table will include incidences of adverse events for each regimen and overall.

All AE summary tables will be listed in the SAP.

AEs will be summarized using preferred term and primary system organ class.

Individual results for clinical hematology and serum chemistry laboratory tests that are outside of normal range and results that meet Takeda predefined criteria for markedly abnormal values will be considered as clinically significant and identified in summary tables, if applicable. Observed values and change from Baseline will be summarized by regimen. All laboratory values will be presented in the data listings.

Individual vital sign values that meet the Takeda predefined markedly abnormal criteria will be considered as clinically significant and identified in a summary table. The vital sign measurements at predefined time points and change from Baseline will be summarized by regimen. All vital signs data will be presented in the data listing.

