7.11.2 Clinical Laboratory Evaluations

Laboratory samples will be obtained following a minimum 8-hour overnight fast on Day 1 of Period 1 (pre-dose), and Day 4 of Period 4 (or Study Exit in case of early termination), see Appendix A. Baseline will be defined as the Day 1 value.

Laboratory values for hematology, serum chemistry, and urinalysis, see protocol section 9.1.8, will be summarized by regimen and by all subjects Overall. Individual subject values together with treatment sequence assignment will be presented in data listing; values that meet the Takeda predefined markedly abnormal value (MAV) criteria, [Appendix B](#), and/or outside normal range will be flagged in the data listing. For each laboratory parameter, where possible, the following will be performed:

- Descriptive statistics for change from baseline,

- Number and percentage of subjects with a value outside normal range,
- Number and percentage of subjects with a value meeting MAV criteria.

Individual results for hematology and chemistry laboratory tests that meet the Takeda predefined laboratory markedly abnormal value (MAV) criteria in [Appendix B](#) will be presented in a data listing. If a subject has an MAV for a laboratory test, all visits for that subject for that parameter will be listed.

All clinical laboratory data will be presented in both SI and conventional units in the data listings. Laboratory data outside of the normal reference range will be listed. Out of normal range values and MAVs will be flagged in data listings.

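### The later-value rule in SAP 7.1.3 makes no exception for abnormality counts, so a laboratory endpoint defined as any occurrence after dosing can be undercounted

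*SAP*

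**What the plan says.** The selection rule is in SAP 7.1.3: "If a subject has more than one laboratory value (eg. a repeat laboratory draw) then the latter will be used for data analyses". The sentence before it names two collection points: "Safety laboratory collections (i.e. clinical laboratory evaluations) are obtained Pre-dose on Day 1 (baseline) and Day 4 of Period 4 (post-baseline"). SAP 7.11.2 and SAP Appendix A add a draw at early termination. No day limits are given for the postdose point.

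The endpoint, worded alike in SAP 5.2 and Protocol 5.2.2.2, is: "Percentage of subjects who have clinically significant changes in laboratory tests at least once postdose".

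Protocol 13.1.4 says what is clinically significant for hematology and serum chemistry. It names results outside the normal range and adds: "results that meet Takeda predefined criteria for markedly abnormal values will be considered as clinically significant and identified in summary tables, if applicable".

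For each laboratory parameter, SAP 7.11.2 plans "Number and percentage of subjects with a value outside normal range" and "Number and percentage of subjects with a value meeting MAV criteria". It does not say whether a value that has been replaced by a repeat still counts.

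Retesting is foreseen. Protocol 9.1.8 says: "A clinically significant laboratory abnormality that has been verified by retesting will be followed until the abnormality returns to an acceptable level". The same section asks for follow-up tests within 7 days when ALT or AST exceeds 3 x ULN, and Protocol 10.1.3 allows repeat testing to verify or monitor an abnormality.

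**The concern.** An endpoint that asks whether something happened at least once needs every postdose value. A rule that keeps only the later value answers a different question: whether the abnormality was present at the last draw. Abnormal results are the ones most likely to be repeated, so the rule acts mainly on the subjects the endpoint is meant to find. At stake is whether the tabulated safety percentage is the one that the protocol and SAP define. The pharmacokinetic analysis does not use these data.

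**Working it through.** The plan states no figure for this endpoint, so there is nothing to reproduce. The check applies the SAP's rule to the SAP's counts.

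**Inputs**
- Selection rule: SAP 7.1.3.
- Scheduled draws: predose in Period 1, then study exit or early termination (SAP 7.1.3, SAP 7.11.2, SAP Appendix A with footnote h).
- Counts: SAP 7.11.2, per parameter.
- MAV limit for ALT and AST: above 3 x ULN (SAP Appendix B).
- Subjects: 72 (SAP 6.0). Default denominator: subjects with non-missing data (SAP 7.1).

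**Step 1: scope of the rule.** Read literally across the whole study, the rule would discard every Day 1 baseline as soon as an exit value existed, and no change from baseline could be calculated. It is workable only per time point, and it is read that way below.

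**Step 2: source of a second postdose value.** Only one postdose draw is scheduled. A second postdose value can therefore come only from a repeat or unscheduled test, which is the case the rule addresses.

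**Step 3: apply both rules to a pair of values at the postdose time point.**

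| First value | Repeat | Later-value rule | Any-value count |
|---|---|---|---|
| normal | normal | not counted | not counted |
| normal | abnormal | counted | counted |
| abnormal | abnormal | counted | counted |
| abnormal | normal | **not counted** | **counted** |

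The rules differ in one row only, and there the later-value rule gives the lower count. The denominator is the same under both rules, so the percentage can only fall or stay the same.

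The two counts behave differently. Take a hypothetical first ALT of 4 x ULN. A repeat at 2 x ULN removes the subject from the MAV count but not from the out-of-range count. A repeat at 1 x ULN removes the subject from both.

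**Step 4: size.**
- Shift per affected subject in a per-parameter row = 1/n, where n is the number with a postdose value. With n = 72: 1/72 = 1.39, or 1.4 percentage points.
- Shift in the endpoint = 1/n if the subject has no other abnormal parameter, and 0 otherwise. The endpoint covers all laboratory tests together.
- Total shortfall in a row: let p be the share with any abnormal postdose value, and q the share of those whose later value is normal. The reported share is p(1 - q), so the shortfall is pq, which lies between 0 and p. The documents give neither p nor q.

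**The case against.** Four arguments can be made on the other side.

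- **The counting section may already mean any value.** SAP 7.11.2 counts subjects with a value outside the limits, which can be read as any value. That reading is possible. However, SAP 7.1.3 decides which value enters the analyses, and SAP 7.11.2 does not set it aside. At best, two programmers could produce different percentages from the same data.
- **The abnormal value is not lost.** This stands. SAP 7.11.2 flags out-of-range and MAV results in listings and lists all visits for a subject with an MAV. Protocol 9.1.8 requires laboratory abnormalities to be recorded as adverse events, and the adverse event tables count any occurrence. But a listing is not a percentage, and tables by system organ class and preferred term are not the laboratory endpoint.
- **Several things must coincide.** There must be a repeat, its result must be normal, and it must be assigned to the same time point. This also stands, and it limits the importance of the point. For an ALT or AST follow-up some days after study exit, the SAP does not say whether the draw belongs to the exit time point, so that example is conditional.
- **The planned counts are per parameter, while the endpoint spans all tests.** This is correct. It limits the effect on the endpoint, and it shows that correcting the per-parameter counts alone would not produce the endpoint percentage.

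**Conclusion.** The point holds and is minor. As written, SAP 7.1.3 can turn an any-occurrence endpoint into a last-value one, and the error is an undercount or nothing. The size is 1.4 points per affected subject in a per-parameter row, assuming that the rule works per time point and that all 72 subjects have a postdose value. In the endpoint it is the same only where that subject has no other abnormal parameter. The total cannot be derived, and no affected subject may occur.

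Three stronger readings are tempting, but the documents do not support them.

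- A reader might infer that abnormal results disappear from the study report. They do not: listings and adverse event records keep them.
- A reader might enlarge the shift by removing the planned 14% drop-outs from the denominator. The plan schedules a laboratory draw at early termination, so drop-outs are meant to contribute a postdose value.
- A reader might quote a larger shift within a regimen, since results "will be summarized by regimen and by all subjects Overall". That requires assigning the single exit draw to one regimen, and the SAP does not say how this is done.

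The summary is descriptive and additional, and the bioequivalence conclusion does not depend on it.

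**What to change.** In SAP 7.1.3, state that the later-value rule applies within a time point and only to descriptive and change-from-baseline statistics.

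In SAP 7.11.2, state that the out-of-range and MAV counts use all postdose values (scheduled, early-termination, repeat and unscheduled), with each subject counted once per parameter. Add one row for the endpoint: subjects with a clinically significant value in any parameter at least once after dosing, each subject counted once.

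The cost is a sentence in SAP 7.1.3, a sentence and one table row in SAP 7.11.2, and slight extra programming. The reported percentages may be higher than under the present rule. Data collection and the pharmacokinetic analysis do not change.
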